### Assessment of CESM images

Paired images will be examined to see if the tumour has been enhanced by the contrast media and to assess its extent. Images will also be assessed for additional foci and contralateral lesions.

### Comparison of CESM and MRI

CESM images and MRI images will be anonymised and read by different readers - CESM images will be reported without the knowledge of the MRI results and vice versa. Mammography and ultrasound images will be available. A completed report on a proforma will be the basis for statistical analysis.

### **Analysis**

Analysis will be undertaken to determine the impact of CESM on patient management decisions (actual or hypothetical). These will be extracted from details recorded on the proforma.

We will also compare the sensitivity and specificity of CESM and MRI on a per lesion basis - including comparison of the maximum dimension of the index tumour - as assessed by independent readers and compared with surgical histopathology.

Analysis of results will also be undertaken in order to inform further study, e.g. sample size and power calculations, and will include an assessment of clinical technique and study procedures from staff questionnaires.

### 8.4.1 Informed Consent

Eligible patients for this study will be identified in the out-patient clinic by members of the breast team. Patients will be given written and verbal information about the study. Consent will be taken by experienced Research Radiographer or Research Nurse. Following their CESM imaging, patients will return to normal standard of care. Safety reporting requirements will end 72 hours after the procedure.

# 8.4.2 Definition of End of Study

The study will end once the last patient recruited has undergone surgery and the surgical histopathology results are available.

# 9. SAFETY REPORTING

### 9.1 Definition of Serious Adverse Events

A serious adverse event is any untoward medical occurrence that:

- Results in death,
- · Is life-threatening,

- Requires inpatient hospitalisation or prolongation of existing hospitalisation,
- Results in persistent or significant disability/incapacity, or
- Is a congenital anomaly/birth defect.
- Other important medical events\*

\*Other events that may not result in death, are not life threatening, or do not require hospitalisation, may be considered a serious adverse event when, based upon appropriate medical judgement, the event may jeopardise the participant and may require medical or surgical intervention to prevent one of the outcomes listed above.

After injection into an artery or vein, it is uncommon (1% risk = 1-10 in 1,0000) to experience pain and discomfort

Rare effects (0.1% risk=1-10 in 10,000) include diarrhoea, irregular heartbeat, kidney problems, cough, fever, general discomfort or dizziness

Very rare (0.01%=less than1in 10,000) include seizures (fits), clouding consciousness, disturbance of senses like touch, trembling, flushing, difficulty breathing including severe breathing difficulty due to fluid in the lungs, short term brain disorders (encephalopathy), short term memory loss, coma and stupor or myocardial infarction.

Any allergic or anaphylactic reactions to the contrast media used in CESM are likely to occur soon after the injection. These will be managed according to local policies by members of the breast team. Minor reactions, e.g., skin rashes, hives (urticaria), itching (pruritus), nausea, dizziness, runny nose (rhinorrhea), brief retching and /or vomiting will be monitored until symptoms have alleviated or further action is needed.

Moderate reactions, e.g. headache, persistent vomiting, wheezing (mild bronchospasm), palpitations, facial swelling, raised blood pressure (hypertension), abdominal cramps; may require an injection of antihistamine and/or adrenaline. An emergency drugs pack will be available in the room during CESM procedures for this purpose.

In the exceptional event of a serious reaction which has the potential to be life-threatening, e.g. difficulty breathing (overt bronchospasm), chest pain, irregular heartbeat (arrhythmia), collapse, seizure, cardiac arrest; a 'crash' call will be made to summon the emergency medical team.

# 9.2 Reporting Procedures for Serious Adverse Events

A serious adverse event (SAE) occurring to a participant will be reported to the REC that gave a favourable opinion of the study where in the opinion of the Chief Investigator the event was: 'related' – that is, it resulted from administration of any of the research procedures; and 'unexpected' – that is, the type of event is not listed in the protocol as an expected occurrence. Reports of related and unexpected SAEs should be submitted within 15 days of the Chief Investigator becoming aware of the event, using the NRES report of serious adverse event form (see NRES website).

# 9.3 Expected Adverse Events

The following adverse events are known possible side effects of CESM procedure. They are generally not serious in nature and will not be recorded as part of this study.

- Bruising from site of injection
- Allergic reaction to contrast media

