The pathway for women randomised to receive usual care will be the same as for those randomised to receive CESM, excluding the CESM procedure, i.e. they will undergo biopsy during their initial clinic visit and results will be discussed at the MDT where a decision regarding their future management will be made.

A flowchart illustrating patient pathways during the CONTEND Study can be found in Appendix I of this document.

A proforma will be used for each case to record patient pathway, results of biopsies and MDT patient management decisions.

Staff will be asked to provide feedback on patient acceptability and ease of undertaking the CESM procedure. They will also be asked to record any incidents of note, e.g. patient related problems; impact on clinic; issues with equipment. Time taken to undertake the examination will be recorded.

In order to compare the diagnostic accuracy of CESM with MRI, CESM images and MRI images will be anonymised and read by different readers - CESM images will be reported without the knowledge of the MRI results and vice versa. Mammography and ultrasound images will be available. A completed report on a proforma will be the basis for statistical analysis.

Histopathology data collected following surgery or from core biopsy if surgery is not undertaken and will be used as the gold standard for measurement of tumour size and extent of disease. If the patient is having primary drug therapy, tumour size will be determined from the mammogram.

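### Section 9.3 exempts allergic reactions to contrast from recording with no seriousness limit, so as written a serious one needs neither a study record under 9.3 nor a REC report under 9.2

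*Protocol*

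**What the plan says.** Four parts of the protocol bear on how a reaction to the contrast is recorded and reported.

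- **Section 9.3 (Expected Adverse Events)** names two known side effects of the procedure: bruising at the injection site and "Allergic reaction to contrast media". Of both it says: "They are generally not serious in nature and will not be recorded as part of this study".
- **Section 9.1 (Definition of Serious Adverse Events)** opens its definition with "A serious adverse event is any untoward medical occurrence that" and lists the seriousness criteria, life-threatening events among them. It adds a category for other important medical events. The same section then says "Any allergic or anaphylactic reactions to the contrast media used in CESM are likely to occur soon after the injection" and sorts reactions into minor, moderate and serious. The last grade is introduced by "In the exceptional event of a serious reaction which has the potential to be life-threatening", and its examples include overt bronchospasm, collapse and cardiac arrest.
- **Section 9.2 (Reporting Procedures)** requires a REC report for an SAE that the Chief Investigator considers both related and unexpected. Unexpected means that "the type of event is not listed in the protocol as an expected occurrence".
- **The synopsis (section 5, Study Design)** says of staff: "They will also be asked to record any incidents of note, e.g. patient related problems".

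Two further provisions matter. Section 8.1 (Subject withdrawal criteria) withdraws women made unwell by the contrast or the procedure and keeps the data of withdrawn women out of the analysis. Section 8.4.1 ends safety reporting 72 hours after the procedure.

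**The concern.** The injection of iodinated contrast is what the CESM arm adds to usual care, and an allergic reaction is the harm most specific to it. Section 9.3 treats this harm as a single class, calls it mostly non-serious, and takes the whole class out of the study record. Saying that such events are mostly not serious concedes that some are, yet the exemption makes no exception for those.

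Two things are at stake. One is oversight: a serious reaction caused by a research procedure could stay outside both the study record and the REC's view. The other is the pilot's own purpose. The Rationale in section 6 says that the study is to assess acceptability of the test and to inform a multicentre trial. How often women react to the injection, and how badly, is part of that, and the exemption together with the withdrawal rule in 8.1 removes it from the analysed data.

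**Working it through.** No figure in the plan is in dispute and no arithmetic applies. The check is to follow an event through the rules as they stand.

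**A serious allergic reaction to the study contrast**

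1. *Is it serious under 9.1?* Yes. The top grade in 9.1 is potentially life-threatening. Such a reaction meets the life-threatening criterion or, failing that, the category of other important medical events that may jeopardise the participant.
2. *Is it related under 9.2?* Yes. The contrast is given as part of the research procedure.
3. *Is it unexpected under 9.2?* No. The test is whether "the type of event is not listed in the protocol as an expected occurrence". Section 9.3 lists the type, "Allergic reaction to contrast media", without qualification, and 9.2 has no second test for severity or seriousness.
4. *Is a REC report required?* No. Section 9.2 says: "Reports of related and unexpected SAEs should be submitted within 15 days of the Chief Investigator becoming aware of the event". An event that fails the unexpected test falls outside this.
5. *Is it recorded?* Not under 9.3, whose exemption covers every listed event. No other provision sets out how SAEs are to be recorded.
6. *Does it reach the analysis?* Not if the woman is withdrawn under 8.1, because her data are then not used.

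**Comparison of cases**

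| Event | Listed in 9.3? | REC report under 9.2 as written | Recorded under 9.3 as written |
|---|---|---|---|
| Minor allergic reaction | Yes | Not an SAE | No |
| Serious allergic reaction | Yes | Not required | No |
| Serious contrast-related event that is not allergic (for example a seizure) | No | Required, if 9.3 is taken as the list of expected events | Not exempted |

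The second row is the fault. A serious allergic reaction is handled like a minor one, although 9.1 grades them apart.

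**Conflict with the synopsis.** A contrast reaction is plainly a patient-related problem. The synopsis asks staff to write such incidents down, while 9.3 says that they will not be recorded. Both instructions cannot be followed for the same event.

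**Effect of limiting the exemption.** If 9.3 covered only non-serious reactions, step 3 would no longer exclude a serious reaction by its type, and step 5 would require a record. The event would then be assessed under 9.2 like any other SAE.

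**The case against.** The best defence is that 9.3 was meant to excuse routine minor events only, and that serious ones belong to 9.1 and 9.2, where the Chief Investigator's opinion governs. That may well be the intention. The wording does not secure it: 9.3 has no such limit, and the Chief Investigator's opinion is applied to a test that refers back to the protocol's own list of expected events. Nor is it a fault in itself that only related and unexpected SAEs go to the REC. The fault lies in a listed type with no seriousness limit, joined to an instruction not to record.

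It can also be said that the staff feedback in the synopsis, or the annual REC report in section 11.2, would bring a serious reaction to light. They might. But the feedback is about acceptability and workflow and does not override 9.3, and an event that is not formally recorded would not reliably reach an annual report.

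Three stronger readings are tempting and are not supported.

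- *That nearly every contrast-related SAE counts as expected.* This would require the side effects described in 9.1, such as seizures, coma and myocardial infarction, to be events listed as expected. Section 9.3 is the section with that title and has two items, while 9.1 calls those effects very rare and calls a serious reaction exceptional. A serious event that is not allergic is, on the natural reading, still reportable.
- *That the study would record no reactions at all, whatever happened.* The synopsis asks staff to note incidents, and 8.1 requires women with ill-effects to be identified so that they can be withdrawn. The recording rules conflict; they do not guarantee an empty record.
- *That 8.1 cancels SAE reporting.* It governs use of data in the analysis and nothing more.

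**Conclusion.** The point holds for serious allergic reactions to the study contrast. As sections 9.1 to 9.3 are written, such a reaction is an SAE that needs no REC report under 9.2 and no study record under 9.3, and the synopsis gives a contrary instruction on recording. This is a rule stated wrongly, not a detail left to another document.

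The scope is one of the two items in 9.3, in the approximately 50 women due to undergo CESM (section 10.1). The protocol gives no frequency for allergic reactions, so no expected number of affected women is offered. The conclusion rests on reading 9.3 as the protocol's list of expected events and on taking its exemption literally. If the sponsor intended it for non-serious reactions only, the text should say so. It should be changed, because it touches participant safety and REC oversight and the remedy is cheap.

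**What to change.** 1. **Reconcile 9.1, 9.2 and 9.3 (the necessary change).** State in 9.3 that the expected status and the exemption from recording apply only to non-serious reactions. State in 9.2 that any contrast reaction meeting the SAE definition in 9.1 is recorded and assessed for REC reporting. Bring the synopsis instruction on incidents into line with this.
2. **Record and tabulate contrast reactions (advisable for the pilot's aims).** Enter each reaction on the CRF within the 72-hour window already set in 8.4.1, using the minor, moderate and serious grades already in 9.1. Tabulate them for all women injected, and state in 8.1 that withdrawal does not remove a woman from this safety table.

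The cost is a wording amendment with REC approval, one CRF line for about 50 women, and possibly an occasional extra REC report. The second item goes further than the inconsistency strictly requires; its justification is that the pilot is meant to assess acceptability. Neither item alters how reactions are managed clinically.

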### 10. STATISTICS

## 10.1 The Number of Participants

There will be approximately 100 participants in order to provide 50 who will undergo CESM.

# 10.2 Analysis of Endpoints

Data from all eligible subjects will be included in the analyses. These will be patients for whom we have data from MRI, CESM and surgical histopathology.

Statistical significance of differences between CESM and MRI will be calculated using McNemar's test . Receiver operating characteristic (ROC) curves will be constructed for both imaging modalities.

Agreement between maximum lesion diameter based on CESM and MRI or CESM and histopathology will be expressed in Bland-Altman plots.

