## 5.

# STUDY SYNOPSIS **Study Title** An assessment of the impact of **CONT**rast **EN**hance**D** Spectral Mammography (CESM) on patient management and comparison with MRI (CONTEND Study) Internal ref. no. RADIOL/2015/CONTEND **Study Design** The aim of this pilot study is to establish the Contrast Enhanced Spectral Mammography (CESM) technique and study procedures. Results of this pilot and feedback from staff will inform Phase 2 of the study which will be a larger, multi-centre, randomised control trial. The study will be undertaken by members of the Cambridge Breast Unit (CBU) at Addenbrooke's Hospital, Cambridge using CESM technology provided by GE Healthcare as an upgrade to the GE Senographe Essential digital mammography system. This technology is already established throughout the world and has FDA approval and is CE marked. This will be a randomised, sequential cohort study. Following standard mammography and ultrasound all women with lesions of suspicion 3, 4 or 5 will be randomised to either receive CESM in addition to their assessment procedure or to receive usual care. Sealed envelopes will be held at CBU reception desk containing either 'CESM' or 'Usual Care' and one will be selected at random to determine to which arm of the study the woman is allocated. After providing informed consent, those women randomised to receive CESM will undergo the procedure either during the same clinic visit or on a day following the initial clinic visit. This will be dependent upon clinic time and staff availability and the woman's own preferences / circumstances. The index lesion and any additional disease detected by CESM will be biopsied as appropriate and results will be discussed at the multidisciplinary meeting (MDT). For those with biopsy confirmed disease a decision will be made at that meeting regarding conservation surgery, mastectomy or neo-adjuvant therapy. For those with benign disease

confirmed by core biopsy standard care will be followed.

MRI will be performed on appropriate women in line with standard practice. Additional disease detected by MRI will be biopsied if this will influence patient management. Biopsies will be undertaken using either ultrasound or MRI guidance. These cases will be discussed at the MDT and a decision made regarding conservation surgery, mastectomy or neo-adjuvant therapy.

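### Section 10.2 states one analysis set without scope: read literally it holds no usual-care women, and read as the CESM-versus-MRI set it still drops unoperated women, against the synopsis rules on reference standard

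*Protocol*

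**What the plan says.** Under the heading Analysis of Endpoints, section 10.2 opens with "Data from all eligible subjects will be included in the analyses" and continues: "These will be patients for whom we have data from MRI, CESM and surgical histopathology". It then names McNemar's test and ROC curves for CESM and MRI, and ends: "Agreement between maximum lesion diameter based on CESM and MRI or CESM and histopathology will be expressed in Bland-Altman plots". The protocol gives no other analysis set.

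Other parts of the protocol bear on this rule:

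- **Design.** Sections 7.1 and 8.1 describe a randomised study of what adding CESM does to management, with about 50 women per arm. Section 7.1 expects an earlier definitive decision.
- **Usual care (section 5).** "The pathway for women randomised to receive usual care will be the same as for those randomised to receive CESM, excluding the CESM procedure".
- **MRI (section 5).** "MRI will be performed on appropriate women in line with standard practice". The Rationale in section 6 says that UK use is selective.
- **Management data (section 5).** "A proforma will be used for each case to record patient pathway, results of biopsies and MDT patient management decisions".
- **Reference standard (section 5).** The first choice is histopathology after an operation; the fallback is "core biopsy if surgery is not undertaken and will be used as the gold standard for measurement of tumour size and extent of disease". Then: "If the patient is having primary drug therapy, tumour size will be determined from the mammogram". The synopsis also plans to confirm false positives at 6 months.
- **Reference standard elsewhere.** The secondary endpoints in sections 5 and 8.2, and the Analysis paragraph of section 8.4, name surgical histopathology only.
- **Withdrawal (section 8.1).** Women who have ill-effects or cannot complete the procedure are withdrawn. Data from withdrawn women are not analysed.

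**The concern.** An analysis set that requires a CESM result cannot contain a woman from the arm that does not receive CESM. If the sentence governs every endpoint, the management question loses its control arm. It also loses CESM women who had no MRI or no operation, although a change of plan prompted by CESM needs neither.

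If the sentence governs only CESM versus MRI, the difficulty shifts to the reference standard. Women with benign biopsies return to standard care under the synopsis, so unoperated women are to be expected. They carry information on specificity and false positives, both of which are secondary outcomes. Removing them lets the decision to operate, which may depend on the imaging, determine who is counted.

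The withdrawal rule adds an exclusion that depends on a procedure only one arm undergoes. The results are meant to inform the sample size and power of a multicentre trial, so errors here would carry forward.

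**Working it through.** **1. The plan's own figure.** Sections 8.1 and 10.1 want 50 women with CESM. At equal allocation, 50 / 0.5 = 100, which matches the stated total of about 100. No alpha, power or effect size is given.

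**2. Literal reading of section 10.2.**
- Usual care: 50 × 0 = 0 women retained, because none has CESM. This needs no assumption.
- CESM arm: retained = 50 × m × s, with m the share having MRI and s the share having surgery. The protocol gives neither. Assume m from 0.2 to 0.8, s from 0.4 to 0.8, and independence.
  - Low: 50 × 0.2 × 0.4 = 4.
  - Middle: 50 × 0.6 × 0.6 = 18.
  - High: 50 × 0.8 × 0.8 = 32.
- Effect on precision, for an assumed management-change rate of 20% (Wilson 95% interval): 10/50 gives 11.2–33.0%, 4/20 gives 8.1–41.6%, and 2/10 gives 5.7–51.0%.

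**3. Narrow reading: CESM versus MRI only.** The passages side by side:

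| Situation | Synopsis (section 5) | Section 10.2 |
|---|---|---|
| Not operated | Core biopsy serves for size and extent | Woman not in the set |
| Primary drug therapy | Size taken from the mammogram | CESM diameter plotted against histopathology, no exception |
| False positives | Confirmed at 6 months | Only women with surgical histopathology counted |

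Section 7.2 lists index lesion size and total extent within the sensitivity and specificity objective, so the first two rows fall inside the accuracy analysis.

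Numbers at the middle assumption: accepting core biopsy keeps 50 × 0.6 = 30 women with CESM and MRI, against 18 under section 10.2.

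Verification bias in specificity: let *sp* be the true specificity, and let *r* be the surgery rate in benign lesions called positive divided by that in benign lesions called negative. Among operated benign lesions,

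observed specificity = sp / (sp + (1 − sp) × r).

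With sp = 0.80:
- r = 0.25: 0.80 / (0.80 + 0.05) = 94%
- r = 0.5: 0.80 / (0.80 + 0.10) = 89%
- r = 1: 0.80 / (0.80 + 0.20) = 80%
- r = 2: 0.80 / (0.80 + 0.40) = 67%
- r = 3: 0.80 / (0.80 + 0.60) = 57%

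The protocol does not fix r. Imaging that looks worse may lead to surgery (r above 1). Equally, a positive call that biopsy shows to be benign goes to standard care (r below 1). The model treats surgery as a lesion-level event, whereas section 10.2 selects patients, so it shows the possible size and not a forecast.

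**4. Withdrawal rule.** Section 8.4 randomises the woman first and then arranges CESM, so failure to complete CESM comes after randomisation and can occur only in that arm. With 10 changes in 50 women, the rate is 20.0%. If 1 woman without a change is dropped, 10/49 = 20.4%; if 5 are dropped, 10/45 = 22.2%. If the dropped women had had a change, the rate would fall instead.

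**The case against.** The strongest reply is that section 10.2 was never meant for the management endpoint. Every method after the sentence is paired, and MRI, CESM and surgical histopathology together supply what those methods need. Sections 5, 8.2 and 8.4 describe the management analysis separately, with the proforma as its source. This largely stands. A reader might infer that the protocol plans to discard its control arm; the documents do not support that. What they show is a sentence without a scope.

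A reader might also infer that a between-arm test has been lost. None is named. The synopsis words the primary endpoint as disease found by CESM, with actual or hypothetical decisions, which can be measured only in the CESM arm. The total of 100 is derived only from the need for 50 CESM examinations. Randomisation, the objective in section 7.1 and a proforma for every case still make it unreasonable to leave usual-care data outside the stated set.

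On the reference standard, four places agree on surgical histopathology, and the core-biopsy rule is worded for size and extent only. The 6-month check could serve an unresected additional lesion in an operated woman. So the firm contradiction concerns size and extent in unoperated women, and size under primary drug therapy. A contradiction over sensitivity and specificity as a whole is not established.

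It is tempting to say that the surgery-only set lowers specificity. The documents do not support a direction.

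On withdrawal, the voluntary part applies to both arms. Whether a CESM cancelled by the creatinine check counts as not completed is a matter of interpretation.

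**Conclusion.** The point holds in this form. Section 10.2 states a rule that, followed to the letter, leaves 0 of about 50 usual-care women and an unknown part of the CESM arm (4 to 32 of 50 under the assumed, independent MRI and surgery rates). On the likelier reading, it conflicts with the synopsis on size and extent in unoperated women and on size under primary drug therapy. It also rests accuracy on operated women only, with a verification bias of unknown sign: 94% to 57% for a true specificity of 80%, over an assumed r of 0.25 to 3. The one-arm withdrawal exclusion is real but small, 20.0% becoming 20.4–22.2% in the example.

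The textual defects depend on none of the assumed rates. These are rules the protocol itself states, so an unseen statistical analysis plan would not remove the conflict from the protocol. Severity is should-fix: this is a single-centre pilot that states no power, and clearer wording cures most of the problem.

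**What to change.** 1. Confine the analysis-set sentence in section 10.2 to the accuracy comparison of CESM with MRI.
2. State that management decisions on the proforma are summarised for all randomised women by allocated arm, whether or not they had MRI, surgery or a completed CESM. Describe extra disease that CESM finds and that alters management within the CESM arm only.
3. Amend the withdrawal paragraph in section 8.1 so that data from women who could not complete CESM stay in the management analysis where consent allows.
4. For accuracy, include women with both CESM and MRI. Use surgical histopathology if they were operated on and core biopsy otherwise, with the planned 6-month follow-up for false positives. Report the surgery-only set as a sensitivity analysis. Reconcile sections 5, 8.2, 8.4 and 10.2 on the reference standard, including tumour size under primary drug therapy.
5. At the same time, reconcile the end of study: sections 5 and 8.1 put it at completion of data analysis, section 8.4.2 at the last surgical histopathology. This is minor and changes no estimate.

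The cost is one protocol amendment with sponsor and REC review, and a mixed reference standard for accuracy that must be reported as such. The proforma, the biopsy results and the 6-month confirmation are already planned, the last only in the synopsis.
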